10.3.5 Interim Analyses

Cohorts A1 and B1: No interim analysis for futility is planned, as the Cohorts are expected to be fully enrolled when the OS endpoint becomes available. However, in Module A if other indications are stopped for futility, enrollment in Module B may be initiated based on recommendations of the Steering Committee.

Cohorts A2 and B2: The interim futility analysis for Cohorts A2 and B2 (HGG) will be conducted using PFS(6) and after at least 8 participants have been followed for 6 months. In addition, all other available efficacy data will be evaluated in the futility analysis.

Cohorts A3 and B3: An interim analysis based on PFS(6) for futility only will be conducted after at least 8 of the planned number of participants are enrolled with 6 months follow-up. In addition all other available efficacy data will be evaluated in the futility analysis.

Cohorts A4 and B4: No interim analysis for futility is planned as the sample size is too small.

Cohorts A5 and B5: No interim analysis for futility is planned as it is comprised of many diverse histologies. However, in Module A if other indications are stopped for futility enrollment in Module B may be initiated based on the recommendation of the Steering Committee.

For Cohorts 2 and 3: the Bayesian statistical methodology is described in Bayesian Adaptive Methods for Clinical Trial by Berry et al published in Chapman and Hall (2011) and is outlined here with adaptations from Lee and Liu A predictive probability design for phase II cancer clinical trials.

Cohort 4 has a smaller sample size than the other cohorts (n=10) so it is not appropriate to add an interim analysis for futility. For Cohorts 2 and 3: The Bayesian statistical methodology is described in Bayesian Adaptive Methods for Clinical Trial by Berry et al published in Chapman and Hall (2011) and is outlined here with adaptations from Lee and Liu REF A predictive probability design for phase II cancer clinical trials. Clinical Trials. 2008 5(2):93-106.

- 1) Once 8 subjects have been followed for at least 6 months a Cox proportional hazards model will be fit to interim data and estimate of hazard rate obtained.
- 2) Based on memoryless property of exponential survival times will be generated for each subject conditional on the observed data using the estimated hazard rate and one-sample log rank test applied to the fully enrolled cohort. The simulated trial will be declared success if log rank is significant.
- 3) Simulations will be repeated 1000 times. The predictive probability of success is defined as the proportion of simulated trials that are declared success based on observed interim data.
- 4) If predictive probability of success is <20%, futility may be declared. The totality of data will be considered in any decision to stop the cohort.

Detailed simulations will be described in the Statistical Analysis Plan.

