10. STATISTICAL CONSIDERATIONS

10.1 Sample Size Determination

[REDACTED]

[REDACTED]

[REDACTED]

[REDACTED]

[REDACTED]

By applying the above methodology, the intended target number of participants (N) for cohort 1-4 are obtained as follows:

Cohort 1: 22 participants are required (17 events) for each cohort. This assumes 80% power with a one-sided Type 1 error of 10%, a historical median OS of 9 months (██████████), 1-year accrual, 2-year follow-up, and a target effect size of median OS 15 months.

Cohort 2: 15 participants are required for each cohort. This assumes 80% power with a one-sided Type 1 error of 10%, a historical PFS(6) of 18% (██████████), one-year accrual, one-year follow-up, a target PFS(6) of 38%. An interim analysis based on PFS(6) for futility only will be conducted after at least 8 of the planned number of participants are enrolled with 6 months follow-up. In addition, all other available efficacy data will be evaluated in the futility analysis. The method is adapted according to ██████████. Details of the futility criteria and simulations will be contained in the Statistical Analysis Plan (SAP).

Cohort 3: 15 participants are required for each cohort. This assumes 80% power with a one-sided Type 1 error of 10%, 1-year accrual and 1-year follow-up, a historical median PFS(4) of 18% and a target PFS(4) of 38% (see ██████████, equivalent to PFS(6) of 23%). An interim analysis based on PFS(6) for futility only will be conducted after at least 8 of the planned number of participants are enrolled with 6 months follow-up. In addition all other available efficacy data will be evaluated in the futility analysis.

Cohort 4: 10 participants are required for each cohort. This assumes at least 80% power with a one-sided Type 1 error of 10%, a historical median PFS of 2.1 months (see etoposide arm of ██████████), 1-year accrual, 1-year follow-up, and a target median PFS of 4.4 months.

Cohort 5: 18 participants are required for each cohort. Sample sizes each of the expansion Cohorts A5 and B5 is not based on statistical considerations as these cohorts contain various tumor types. However, if the disease control rate at 12 months is 30%, 18 participants provide 21% precision for the estimate.

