Endpoint	Statistical Analysis Methods
Primary	
Cohort A1 and B1: OS	For each cohort separately, OS curve will be estimated using the Kaplan-Meier (KM) method. The distribution of OS in all treated participants will be compared against the historical control of an exponential distribution with median OS 9 months (Cohen, Heideman, et al) using a one-sided one-sample log rank test when approximately 17 events have occurred or after each participant has been followed for at least 24 months. Median OS and the corresponding two-sided 80% confidence intervals using the log-log transformation will be computed.
Cohort A2 and B2: PFS	For each cohort separately, PFS curve will be estimated using the Kaplan-Meier (KM) method. The distribution of PFS in all treated participants will be compared against the historical control of an exponential distribution with median PFS 2.25 months (Hwang, et al) using a one-sided one-sample log rank test when each participant has been followed for at least 12 months. Median PFS and the corresponding two-sided 80% confidence intervals using the log-log transformation will be computed.
Cohort A3 and B3: PFS	For each cohort separately, PFS curve will be estimated using the Kaplan-Meier (KM) method. The distribution of PFS in all treated

Endpoint	Statistical Analysis Methods
	participants will be compared against the historical control of an exponential distribution with PFS(4) equal to .18 using a one-sided one-sample log rank test when either 15 events have occurred or each participant has been followed for at least 12 months. Median PFS and the corresponding two-sided 80% confidence intervals using the log-log transformation will be computed.
Cohort A4 and B4: PFS	For each cohort separately the distribution of PFS in all treated participants will be compared against the historical control of an exponential distribution with median PFS equal to 2.1 months using a one-sided one-sample log rank test when either 10 events have occurred or each participant has been followed for at least 12 months.
Cohort A5 and B5: PFS	For each cohort separately individual PFS will be listed by tumor type after each participant reaches 12 months follow-up. PFS curve will be estimated using the Kaplan-Meier (KM) method for all tumor types (pooled) and selected individual tumor types, if there is enough data.
Secondary	

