7.5.2 Progression Free Survival

For all cohorts, progression free survival (PFS) is defined as the time from first dose to the date of the first documented tumor progression or death due to any cause. Participants who die without a reported prior progression will be considered to have progressed on the date of death. Participants who did not have disease progression or die will be censored at the date of last evaluable tumor assessment. Participants who did not have any on study tumor assessment and did not die will be censored at the first dose date. PFS will be determined by investigators based on RANO criteria. First tumor assessments will occur at week 6 and 12, and will be at every 8 weeks for the first year and then every 12 weeks thereafter until disease progression is documented

7.5.2.1 Progression Free Survival for Cohorts 1

As one of the secondary endpoints of Cohort 1, PFS is estimated by Kaplan-Meier method and the corresponding 95% CI for median PFS will be calculated via Brookmeyer and Crowley methodology using log-log transformation. It will be analyzed at the time of the primary analysis.

7.5.2.2 Progression Free Survival for Cohorts 2 to 4

As the primary efficacy endpoints of cohorts 2 to 4, PFS curve will be estimated using the Kaplan-Meier (KM) method. Median PFS and the corresponding two-sided 80% confidence intervals using the log-log transformation will be computed.

The distribution of PFS for cohort 2 will be compared against the historical control of an exponential distribution with median PFS 2.25 months [REDACTED] using a one-sided one-sample log rank test when each participant has been followed for at least 12 months.

The distribution of PFS for cohort 3 will be compared against the historical control of an exponential distribution with PFS(4) equal to .18 using a one-sided one-sample log rank test when either 15 events have occurred or each participant has been followed for at least 12 months.

The distribution of PFS for cohort 4 will be compared against the historical control of an exponential distribution with median PFS equal to 2.1 months using a one-sided one-sample log rank test when either 10 events have occurred or each participant has been followed for at least 12 months.

In addition, as one of the secondary endpoints, PFS rate at 6 months will be estimated using KM estimates on the PFS curve and its corresponding 95% confidence interval will be derived based on Greenwood formula.

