7.5.3 Subsequent Therapy

Subsequent therapy will be summarized and listed.

- Subsequent Therapy
 - Systemic anti-cancer therapy by drug name
 - Surgery

– Radiotherapy

A by-subject listing of follow-up therapy will be produced for subjects who had any subsequent therapy.

7.5.4 *Interim Analyses*

Cohorts A1 and B1: No interim analysis for futility is planned, as the Cohorts are expected to be fully enrolled when the OS endpoint becomes available. However, in Module A if other indications are stopped for futility, enrollment in Module B may be initiated based on recommendations of the Steering Committee.

Cohorts A2 and B2: The interim futility analysis for Cohorts A2 and B2 (HGG) will be conducted using PFS(6) and after at least 8 participants have been followed for 6 months. In addition, all other available efficacy data will be evaluated in the futility analysis.

Cohorts A3 and B3: An interim analysis based on PFS(6) for futility only will be conducted after at least 8 of the planned number of participants are enrolled with 6 months follow-up. In addition all other available efficacy data will be evaluated in the futility analysis.

Cohorts A4 and B4: No interim analysis for futility is planned as the sample size is too small.

Cohorts A5 and B5: No interim analysis for futility is planned as it is comprised of many diverse histologies. However, in Module A if other indications are stopped for futility enrollment in Module B may be initiated based on the recommendation of the Steering Committee.

Cohort 4 has a smaller sample size than the other cohorts (n=10) so it is not appropriate to add an interim analysis for futility.

For Cohorts 2 and 3: The Bayesian statistical methodology is described in Bayesian Adaptive Methods for Clinical Trial by Berry et al published in Chapman and Hall (2011) and is outlined here with adaptations from [REDACTED] [REDACTED].

- 1) Once 8 subjects have been followed for at least 6 months a Cox proportional hazards model will be fit to interim data and estimate of hazard rate obtained.
- 2) Based on memoryless property of exponential survival times will be generated for each subject conditional on the observed data using the estimated hazard rate and one-sample log rank test applied to the fully enrolled cohort. The simulated trial will be declared success if log rank is significant.

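### Cohort 2 is sized on one historical PFS and tested against another, and the Cox fit in the futility rule gives no constant hazard for its exponential draws

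*Protocol*

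**What the plan says.** **Cohort 2 null.** The protocol synopsis, protocol 10.1 and SAP 5 assume 80% power, one-sided 10% error and a historical PFS(6) of 18%, with "one-year accrual, one-year follow-up, a target PFS(6) of 38" per cent, and arrive at 15 participants. For the final analysis, protocol 10.3.1 states: "The distribution of PFS in all treated participants will be compared against the historical control of an exponential distribution with median PFS 2.25 months". SAP 7.5.2.2 gives the same reference, "an exponential distribution with median PFS 2.25 months". Cohort 3, by contrast, uses PFS(4) of 18% in both places.

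**Futility rule, Cohorts 2 and 3.** The Cohort 2 look "will be conducted using PFS(6) and after at least 8 participants have been followed for 6 months". The Cohort 3 look is likewise described as based on PFS(6). Protocol 10.3.5 and SAP 7.5.4 then list the same four steps:

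1. "Once 8 subjects have been followed for at least 6 months a Cox proportional hazards model will be fit to interim data". The SAP's wording, "a Cox proportional hazards model will be fit to interim data and estimate of hazard rate obtained", matches the protocol's, so the point applies to both documents.
2. The draws come next: "Based on memoryless property of exponential survival times will be generated for each subject conditional on the observed data using the estimated hazard rate". Each completed cohort is then put through the one-sample log-rank test.
3. This is repeated 1,000 times, and the predictive probability is the share of successes.
4. Below 20%, futility may be declared, but "The totality of data will be considered in any decision to stop the cohort".

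**The concern.** A power statement holds only for the null hypothesis that is tested. If Cohort 2 is sized against one historical hazard and tested against a higher one, the test is easier to pass than the sizing section implies. The quoted 80% is then wrong for that test. A therapy no better than the historical rate used for sizing would also be declared promising more often than the nominal 10%.

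In the futility rule, step 2 draws residual times from an exponential distribution and so needs one constant rate. Step 1 is supposed to supply it. No covariate, baseline-hazard estimator or conversion to a constant rate is named, and none of the four steps uses PFS(6). Two statisticians could therefore give the Study Steering Committee different predictive probabilities from the same data.

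**Working it through.** **Inputs.** From protocol 10.1: 15 participants, 12 months accrual, 12 months follow-up, one-sided 10%, 80% power, PFS(6) 18% against 38%. From protocol 10.3.1 and SAP 7.5.2.2: test null with median 2.25 months. Cohort 3: PFS(4) 18% against 38%. Assumed: exponential PFS and uniform accrual.

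**Hazards per month.**
- Sizing null: −ln(0.18)/6 = 0.286, median ln 2/0.286 = 2.43 months.
- Test null: ln 2/2.25 = 0.308, PFS(6) = exp(−6 × 0.308) = 15.7%.
- Target: −ln(0.38)/6 = 0.161.

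**Reproducing N.** Events = (1.282 + 0.842)² / (ln HR)², and N = events / P(event under the target). P(event) = 1 − [exp(−12λ) − exp(−24λ)]/(12λ) = 0.936 with λ = 0.161.
- Sizing null: HR = 0.161/0.286 = 0.564, 13.8 events, N = 14.7. This matches the plan's 15.
- Test null: HR = 0.161/0.308 = 0.523, 10.8 events, N = 11.5. This does not match.

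**Power and false positives at N = 15.** Simulated with Z = (E − O)/√V, where E is the null hazard times total follow-up, O is the observed events, and success is Z > 1.282. The documents' readable text does not fix V. Each range runs from V = E to V = (O + E)/2.

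| Null tested | Power at PFS(6) 38% | Success if true PFS(6) is 18% |
|---|---|---|
| PFS(6) 18% | about 79–81% | about 8–9% |
| Median 2.25 months | about 86–87% | about 13–16% |

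**Step 1.** Without covariates, each event contributes 1/(number at risk) to the Cox partial likelihood. It contains no parameter and depends only on the order of the times. For one data set of 14 participants and 7 events the log partial likelihood is −14.64, and it stays −14.64 when every time is multiplied by 10. Events per person-month fall from 0.124 to 0.0124. The fit therefore carries no information about a rate. What remains is a non-parametric step function for the cumulative baseline hazard, which must still be turned into one number.

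**How much the choice matters.** Three ways of getting a rate were compared: events/person-time; −ln(KM PFS(6))/6; and cumulative baseline hazard divided by longest follow-up. The simulation used the sizing nulls, 20,000 trials with 1,000 draws each, and a look at the 8th enrolment plus 6 months. At least one reading differed on stopping in:
- Cohort 2: 9.3–10.2% at the target, 13.7–14.1% under the null.
- Cohort 3: 7.7–8.3% at the target, 10.0–10.5% under the null.

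One alternative at a time against events/person-time, the disagreement is about 4–10%. Overall stop rates (5,000 trials, V = E):

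| Scenario | Events/person-time | −ln(KM PFS(6))/6 | Cumulative hazard / longest follow-up |
|---|---|---|---|
| Cohort 2 target | 16.3% | 17.2% | 16.4% |
| Cohort 2 null | 78.0% | 77.5% | 75.2% |
| Cohort 3 target | 15.7% | 17.1% | 16.1% |
| Cohort 3 null | 82.3% | 81.3% | 79.3% |

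Dividing by the last event time instead gives 23.0%, 84.4%, 20.1% and 84.7%, a shift of 2.4 to 6.7 points from events/person-time.

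**The case against.** **The rule can be run.** Step 2 is explicitly exponential and so are the nulls, so a competent statistician would use events/person-time. That is fair, and a reader who infers that the rule is unworkable goes too far. One rival reading is weak as well: KM PFS(6) is zero, giving no finite hazard, in 14.7% of Cohort 2 and 42.3% of Cohort 3 null trials. But events/person-time replaces what step 1 says. Part of the SAP's introductory method sentence is blacked out and the outside references cannot be seen, but the four steps are readable.

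**Disagreements are borderline.** In a separate run of 4,000 trials per scenario, about 80% of them had a person-time predictive probability between 5% and 50%. There, the non-binding wording leaves the decision to judgement anyway. This stands, and it limits the size of the second defect.

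**Two nulls in step 2.** A reader might infer that step 2 itself is ambiguous for Cohort 2. It is not: it applies the final test, whose only written null is 2.25 months. The mismatch is between sizing and analysis, and the interim rule inherits it.

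**Inflated type I error.** The 13–16% arises only if true PFS(6) is 18%. It is not the error rate under the test's own null. Nor can a futility-only rule raise type I error.

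**The look comes too late to save enrolment.** About 14.5 of 15 would be enrolled, but only under uniform 12-month accrual and if participants with an event before 6 months do not count among the 8. The text leaves the second point open. Counting early events, or accrual over 18–24 months, gives about 11–13. This is a note, not a defect.

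**Lost power.** If a stop only ends accrual, the loss is 0.5–0.7 points. Losses of 3.2–4.1 points require every stopped cohort to be scored as a failure, and no section says that.

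**Conclusion.** Two statements are wrong as written.

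The more important is the Cohort 2 null. The 80% power and N = 15 belong to PFS(6) 18%, while the planned test uses a median of 2.25 months. The power of that test is about 86–87%, and its success rate is about 13–16% if the sizing null is the truth. This rests on exponential PFS, uniform 12-month accrual, 12 months of follow-up and the two variance forms shown. The documents do not settle which historical figure is right. Cohort 3 has no such mismatch.

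The second is step 1 of the futility rule for Cohorts 2 and 3, which names a model that cannot deliver the constant hazard step 2 needs. The PFS(6) basis of the look also appears in no step. Its consequence is minor: roughly 8–14% any-of-three disagreement, with overall stop rates within about 3 points across the three readings, or up to about 7 for the last-event variant. The disagreement figure depends on the readings and the true rate. Across wider variants, including progression dated on the MRI schedule, it ran from about 4% to 21%. The defect itself does not depend on any simulation.

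**What to change.** 1. **Cohort 2 null.** Choose one historical reference and use it in the sizing (synopsis, protocol 10.1, SAP 5), in step 2 of the interim rule, and in the final test (protocol 10.3.1, SAP 7.5.2.2). State the power that belongs to it, without the non-binding futility rule: about 79–81% against a median of 2.43 months, or about 86–87% against 2.25 months.
2. **Step 1 (protocol 10.3.5, SAP 7.5.4).** Replace the Cox sentence with: *the hazard is estimated under an exponential model as PFS events divided by total follow-up time of all enrolled participants at the look*. Delete the PFS(6) wording for the Cohort 2 and 3 looks, or say how PFS(6) enters.

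The cost is one reconciled reference value and one replaced sentence in each document. Sample size, the 20% cut-off and the trigger for the look stay as they are. If the 2.25-month null is kept, the stated 80% for Cohort 2 must be revised upwards.

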12. APPENDICES

APPENDIX 1 ABBREVIATIONS AND TRADEMARKS

Term	Definition
AA	anaplastic astrocytoma
ADA	anti-drug antibodies
AE	adverse event
AIDS	acquired immunodeficiency syndrome
ALT	alanine aminotransferase
AST	aspartate aminotransferase
AT/RT	atypical teratoid/rhabdoid tumor
AUC	area under the concentration-time curve
BICR	blinded independent central review committee
BMS	Bristol-Myers Squibb
BOR	best overall response
BP	blood pressure
BUN	blood urea nitrogen
C	Celsius
CBC	complete blood count
CFR	Code of Federal Regulations
cHL	classic Hodgkins lymphoma
CI	confidence interval
Cl ⁻	chloride
CLcr	creatinine clearance
cm	centimeter
C _{max} , C _{MAX}	maximum observed concentration
CNS	Central nervous system
CR	complete response
CRC	colorectal cancer
CRF	Case Report Form, paper or electronic
CSF	cerebrospinal fluid
CV	coefficient of variation
DILI	Drug induced liver injury

Term	Definition
DIPG	diffuse intrinsic pontine glioma
dL	deciliter
DLT	dose limiting toxicity
DMC	Data monitoring committee
DNA	deoxyribonucleic acid
DOR	duration of response
ECG	electrocardiogram
eCRF	electronic Case Report Form
EFS	event free survival
eg	exempli gratia (for example)
EOI	end of infusion
EOMES	eomesodermin
ESR	Expedited Safety Report
ETMR	embryonal tumor with multilayered rosettes
FDA	Food and Drug Administration
FFPE	formalin-fixed paraffin-embedded
FLAIR	fast fluid-attenuated inversion recovery
FSH	follicle stimulating hormone
GBM	glioblastoma
GCP	Good Clinical Practice
GFR	glomerular filtration rate
HBsAg	hepatitis B surface antigen
HBV	hepatitis B virus
HCC	hepatocellular carcinoma
HCG	human chorionic gonadotropin
HCV	hepatitis C virus
HCV-RNA	hepatitis C virus-ribonucleic acid
HGG	high grade glioma
HIV	Human Immunodeficiency Virus
HLA	human leukocyte antigen

Term	Definition
HR	heart rate; hazard ratio
IB	Investigator Brochure
ICD	implantable cardioverter defibrillator
ICF	informed consent form
ICH	International Conference on Harmonisation
ICOS	inducible T cell co-stimulator
ie	id est (that is)
IEC	Independent Ethics Committee
IHC	immunohistochemistry
IMAE	Immune-mediated adverse event
IMG	immunogenicity
IMP	investigational medicinal products
IND	Investigational New Drug Exemption
IP	investigational product
ir	immune-related
IRB	Institutional Review Board
IRT	Interactive Response Technology
IU	International Unit
IV	intravenous
K ⁺	potassium
KPS	Karnofsky Performance Score
kg	kilogram
L	liter
LAM	Lactation amenorrhea method
LDH	lactate dehydrogenase
LFT(s)	liver function test(s)
LPS	Lansky Play Score
mg	milligram
MGMT	O ⁶ -methylguanylmethyltransferase
min	minute

Term	Definition
mL	milliliter
MLR	mixed lymphocyte reaction
MRI	magnetic resonance imaging
MS	mass spectrometry
MTD	maximum tolerated dose
µg	microgram
N	number of subjects or observations
N	Nivolumab (BMS-936558)
Na ⁺	sodium
NE	not evaluable
NSCLC	non-small cell lung carcinoma
OR	objective response
ORR	objective response rate
OS	overall survival
PBMC	peripheral blood mononuclear cell
PD	progressive disease
PD	pharmacodynamics
PD-1	Programmed cell death protein 1
PD-L1	Programmed cell death ligand 1
PFS	progression free survival
PK	pharmacokinetics
PO	per os (by mouth route of administration)
PR	partial response
QC	quality control
QD, qd	quaque die, once daily
R ²	coefficient of determination
RANO	Radiologic Assessment in Neuro-Oncology
RBC	red blood cell
RCC	Renal cell carcinoma
RT	radiotherapy

Term	Definition
SAE	serious adverse event
SCLC	squamous cell lung carcinoma
SD	standard deviation; stable disease
SmPC	Summary of Product Characteristics
SOP	Standard Operating Procedures
SSC	study steering committee
t	temperature
T	time
TAO	Trial Access Online, the BMS implementation of an EDC capability
TCR	T cell receptor
TILs	Tumor infiltrating lymphocytes
WBC	white blood cell
WHO	World Health Organization
WOCBP	women of childbearing potential

